7.2.6 Criteria and Procedures for Subject Withdrawal

Subjects can decide to withdraw from the investigation at any time. The Investigator shall ask the reason(s), however subjects have the right to withhold their reason if preferred. The reason for withdrawal should be documented in the subject's source files and the electronic case report form (eCRF), if provided.

The Investigator or Sponsor may also decide to withdraw a subject from the clinical investigation or stop the use of the investigational device if it is considered to be in the subject's best interests.

Subject withdrawal may be for any of the following reasons:

- Adverse Event (AE)
- Device Deficiency (DD)
- CIP or GCP deviation
- Subject withdrew consent
- Subject lost to follow-up
- Subject death
- Sponsor decision
- Investigator decision
- Other (specify)

If a subject is lost to follow-up, every possible effort must be made by the study site personnel to contact the subject and determine the reason for discontinuation. At least 3 separate attempts taken to contact the subject must be documented.

Participating subjects who are withdrawn/discontinued will not be replaced.

7.2.7 Randomisation Procedures

Subjects will not be randomised to a treatment condition. To control for order effects, counterbalancing of the test order will be implemented for the primary and secondary speech perception endpoints. All permutations will be represented evenly across the subjects where possible.

SRT SONrearhalf Test order

Primary: Kanso 3 SCAN 2 FF Zoom (Automated ForwardFocus ON) vs Kanso 3 SCAN 2 (ForwardFocus OFF)

Exploratory (2): Kanso 3 SCAN 2 FF Zoom (Automated ForwardFocus ON) vs Kanso 3 SCAN 2 FF Beam (Automated ForwardFocus ON)

Subjects will be tested in the following order:

Subject ID	1st	2nd	3rd
1, 7, 13, 19	SCAN 2 FF Zoom	SCAN 2 FF Beam	SCAN 2 (FF OFF)
2, 8, 14, 20	SCAN 2 (FF OFF)	SCAN 2 FF Zoom	SCAN 2 FF Beam
3, 9, 15	SCAN 2 FF Beam	SCAN 2 (FF OFF)	SCAN 2 FF Zoom
4, 10, 16	SCAN 2 FF Zoom	SCAN 2 (FF OFF)	SCAN 2 FF Beam
5, 11, 17	SCAN 2 FF Beam	SCAN 2 FF Zoom	SCAN 2 (FF OFF)
6, 12, 18	SCAN 2 (FF OFF)	SCAN 2 FF Beam	SCAN 2 FF Zoom

SRT SON3 Test order

Secondary (1): Kanso 3 SCAN 2 FF Zoom (Automated ForwardFocus ON) vs Kanso 3 SCAN 2 (ForwardFocus OFF)

Exploratory (3): Kanso 3 SCAN 2 FF Zoom (Automated ForwardFocus ON) vs Kanso 3 SCAN 2 FF Beam (Automated ForwardFocus ON)

Subjects will be tested in the following order:

Subject ID	1st	2nd	3rd
1, 7, 13, 19	SCAN 2 FF Zoom	SCAN 2 FF Beam	SCAN 2 (FF OFF)
2, 8, 14, 20	SCAN 2 (FF OFF)	SCAN 2 FF Zoom	SCAN 2 FF Beam
3, 9, 15	SCAN 2 FF Beam	SCAN 2 (FF OFF)	SCAN 2 FF Zoom
4, 10, 16	SCAN 2 FF Zoom	SCAN 2 (FF OFF)	SCAN 2 FF Beam
5, 11, 17	SCAN 2 FF Beam	SCAN 2 FF Zoom	SCAN 2 (FF OFF)
6, 12, 18	SCAN 2 (FF OFF)	SCAN 2 FF Beam	SCAN 2 FF Zoom

CNC Words Test Order

Secondary (2): Kanso 3 (CP1170) vs Kanso 2 (CP1150)

Subjects assigned a study ID including ODD numbers (01, 03, 05 etc) will be tested in the following order:

1. Kanso 3
2. Kanso 2

7.2.7.1 Blinding Procedures

For in-booth speech perception testing, the test order will not be revealed to the study subject. The counterbalancing procedures will be used to ensure that there is a balanced order of test conditions.

7.2.8 Post-investigation Medical Care

All IMD management during the study will be done by the study investigators. Subjects will be able to see their regular clinicians when wearing their own sound processors. At the end of each test session and take-home periods, subjects will return all investigational devices to the investigator and return to using their own sound processors programmed with commercial programming software versions. Subjects will continue to be clinically managed by their regular clinician according to their clinic's standard practice after the clinical investigation has been completed.

7.3 Evaluations and Procedures

7.3.1 Screening/eligibility

- Screening and informed consent: Subjects must be consented to the study and inclusion and exclusion criteria confirmed prior to any study activities starting.
 - Evidence for inclusion criteria #6 (i.e. able to score 30% or more at +15 SNR with CI alone on a sentence in babble test) can be provided from data on file for subjects who had previously participated in clinical investigations at the site.
- Standard eCRFs will be completed, including:
 - Demographics: information about the subjects age and gender identification.
 - Eligibility: itemised confirmation that the subject meets all inclusion and exclusion criteria.
 - Medical history: information about any current or past medical conditions or surgical history.
 - Hearing history: information about the subject's hearing for both ears, including hearing loss, age of onset of initial hearing loss, hearing loss type, history of hearing loss, primary cause of hearing loss and other relevant aspects of the subject's audiological history.
 - Device history: information about the subject's cochlear implant and/or hearing aid usage and amplification history.
 - Concomitant medications/therapies: all prescription and/or over-the-counter medications as reported by the subject.

Screening and Visit 1 procedures may occur at the same visit.

7.3.1.1 Visit 1

- Baseline SSQ: *see Section 7.3.2.6.1.*
- Baseline Device Characteristics Questionnaire: *see Section 7.3.2.6.2.*
- CP1170 Fitting: *see Section 7.3.2.3.*

7.3.1.2 Visit 2

- Fitting optimisation (optional, as required): *see Section 7.3.2.4.*

Visit 2 and Ad Hoc Visit procedures may be conducted on the same day.

7.3.1.3 Ad Hoc Visits

Ad Hoc visits are not tied to any specific visit or timing window and may be repeated to perform any of the following procedures when appropriate, as determined by the investigator:

- Sound processor fitting to initiate a take-home period or fitting optimisation (optional, as required).
- Speech perception evaluations in noise (as required): *see section 7.3.2.1.*
- Speech perception evaluation quiet (as required): *see section 7.3.2.2.*
- Usability interview (as required): *see section 7.3.3.1.*

- Provision or collection of questionnaires, (e.g. the EMA, CP1170 and/or CP1170 Questionnaire; as required).
- If the ad-hoc visit is at the end of a take-home period, study subjects will be asked about their experience with the CP1170 sound processor. Device deficiencies and adverse events experienced during this take home period will be recorded if not already.

A maximum of 20 Ad-Hoc Visits is expected duration of the study.

7.3.1.4 End of Study Visit

- Collection of final SSQ12 Questionnaire following CP1170 use: *see Section 7.3.2.6.1*.
- Collection of any remaining questionnaires (e.g. EMA or CP1170 Questionnaire) provided as part of final take-home period (as required).
- Return devices and study completion: At the end of the study, subjects will return all IMDs and associated components and revert to full-time use of their own device with the commercially available firmware.

The EOS visit can occur on the same day as an Ad Hoc visit.

7.3.2 Performance/Effectiveness

Refer to the Schedule of Events in Section 3 for details of the timing and frequency of the evaluations described in the subsections below.

7.3.2.1 Speech perception in noise

Speech perception in noise will be measured using the Australian Speech Test In Noise (AUSTIN) (Dawson, Hersbach, & Swanson, 2013), which is a test that uses BKB like target sentences presented in adaptive noise. The goal of the speech perception test in noise is to provide the SNR for 50% speech intelligibility. The signal level will be fixed at 65 dB SPL. Sentence in noise tests will be measured using this procedure in the two speaker configurations shown below.

[figure not shown]

Figure 3. Left – SON3 with babble noise from 90, 180 and 270 degrees (3 talkers in total). Right -SONrearhalf with roving babble noise presented from 4 speakers in the rear hemisphere (4 talkers in total). The rear hemisphere will consist of 7 speakers and the 4 noise speakers will change for every sentence in the test list.

In booth speech perception testing will be conducted using the signal processing combinations and hardware listed in Table 2. The order of testing will be conducted according to the counterbalancing outlined in Section 7.2.7.

Table 2. Speech in Noise test conditions (SONrearhalf and SON3). Whisper, WNR, ADRO and ASC will be activated according to user preference.

#	Condition	SNR-NR	Sound Processing	Directionality	ForwardFocus	Comparisons
1	Kanso 3 SCAN 2 FF Zoom (Automated ForwardFocus ON)	✓	SCAN 2	Zoom	ON	Primary: 1 vs 3 in 65 dB SPL SONrearhalf 4TB. Secondary (1): 1 vs 3 in 65 dB SPL SON3 Babble. Exploratory (2): 1 vs 2 in 65 dB SPL SONrearhalf 4TB. Exploratory (3): 1 vs 2 in SON3 Babble
2	Kanso 3 SCAN 2 FF Beam (Automated ForwardFocus ON)	✓	SCAN 2	Beam	ON	
3	Kanso 3 SCAN 2 (ForwardFocus OFF)	✓	SCAN 2	Beam	OFF	

For SONrearhalf and SON3 speech in noise tests, all subjects will be tested unilaterally. That is, unilateral subjects will have their contralateral ear (non-test ear) blocked with an earplug for all test conditions. Subjects with bilateral implants will be tested using the subject's preferred listening ear or if the preferred ear is not known then the first implanted ear will be used as the test-ear.

The subject will be positioned so that the middle-point of two ears is centred at the reference point of the sound field. The loudspeaker should be positioned at the same height as the middle-point of the two ears.

The AuSTIN software will be used to present the test material. The investigator, or suitably qualified delegate will use the software to select:

- Adaptive test (SRT)
- 65 dB SPL presentation level
- Signal from in front (0 degrees)
- Babble noise from either:
 - SONrearhalf: 4 locations in the rear hemisphere. In the SONrearhemi condition, four independent interfering talkers are presented from four locations simultaneously, randomly chosen from seven speakers between 90 to 270 degrees in a rear hemi-field. The noise locations remained fixed for the duration of each sentence and changed two seconds before the next sentence is presented (at the same time as the noise level changed).
 - SON3: 90, 180 and 270 (3 speakers in total)

At the beginning of the test session a practice run of 16 sentences with the first signal processing combination to be tested will be undertaken. This practice run is not required to be repeated if all sentence tests are completed on the same day. The starting point for the first test will be set within 5dB SNR of the practice run result. For signal processing parameters that are expected to produce highly variable results or large differences, a practice run may be required for each signal processing combination. The number of sentences will be 20 for all test runs.

The investigator will record the result on the worksheet and in the Electronic Data Capture (EDC) system.

7.3.2.2 Speech perception in quiet

Speech perception in quiet will be measured using the CNC monosyllabic words (Peterson & Lehiste, 1962) at 50 dB SPL from S0 position (Figure 4). There will be 2 lists per condition. The goal of speech perception assessment in quiet is to compare % words correct for each of the conditions.

Figure 4. Speaker configuration for CNC words in quiet

In booth speech perception testing will be conducted using the input processing combinations and hardware listed in Table 3. The order of testing will be conducted according to the counterbalancing outlined in Section 7.2.7.

Table 3. Speech in Quiet test conditions. Whisper, WNR, ADRO and ASC will be activated according to user preference.

Condition	SNR-NR	Default	ForwardFocus
Kanso 3 (CP1170)	✓	SCAN 2	OFF
Kanso 2 (CP1150)	✓	SCAN	OFF

All subjects will be tested unilaterally i.e., unilateral subjects will have their contralateral ear (non-test ear) blocked with an earplug for all test conditions and subjects with bilateral implants will be tested using the subject's preferred listening ear or if the preferred ear is not known then the first implanted ear will be used as the test-ear. The subject will be positioned so that the middle-point of two ears is centred at the reference point of the sound field. The loudspeaker should be positioned at the same height as the middle-point of the two ears.

The AuSTIN software will be used to present the test material. The investigator, or suitably qualified delegate will use the software to select:

- CNC word test
- 50 dB SPL presentation level
- Signal from in front (0 degrees)
- 2 lists of 50 words each

At the end of each run, the investigator will record the result on the worksheet and in the EDC.

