In study CRC5589/CTC5614, using the Nucleus 6 Sound Processor (Model CP910), speech perception outcomes and acceptance for three different strengths of ForwardFocus integrated with SCAN were compared with SCAN plus SNR-NR (N6 SCAN). Sentence recognition scores with noise in rear half noise was significantly better with all FF programs than N6 SCAN. Word recognition scores in quiet and questionnaire ratings for all ForwardFocus programs were comparable to N6 SCAN. Sentence-in-noise scores obtained with speech and noise presented from the front were non-inferior to N6 SCAN for mild ForwardFocus only. A decrement compared with ForwardFocus Strong was found. Sentence in noise scores with speech presented to the cochlear implant side or from behind the listener with mild FF were inferior to the baseline. Based on these findings the investigators recommended that FF be introduced as a custom programme that could be selected for specific listening conditions.

Study CLTD5606 was designed to assess the effectiveness of ForwardFocus for speech reception in noise compared with the Nucleus 6 SCAN (SCAN + SNR-NR). The study included twenty-five conventional CI recipients. For sentence recognition with four-talker babble from the rear, all three levels of FF (strong, medium and mild) were found to be superior to the Nucleus 6 SCAN. For SWN presented behind the listener FF Strong was demonstrated to be superior to the Nucleus 6 SCAN. When speech and either SWN or four-taker babble were co-located in front of the listener, sentence recognition with ForwardFocus Strong was similar to the Nucleus 6 SCAN. For CNC words in quiet ForwardFocus Strong was inferior to the Nucleus 6 SCAN. The investigators concluded that acceptable performance and safety of the ForwardFocus program can be anticipated for Nucleus 7 Sound Processor users in noisy environments, and the risk versus benefit profile is acceptable when ForwardFocus be used in quiet environments.

The in-house study CLTD5709 investigated the effect of ForwardFocus noise reduction on adult cochlear implant recipients' speech perception scores, listening effort and subjective ratings using the Nucleus 7 Sound Processor. A total of 24 subjects were enrolled in the study.

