6.2 Secondary Objectives

1. To compare adult cochlear implant speech perception in spatially separated speech and noise (SON3) between the CP1170 sound processor programs, SCAN 2 FF (Automated ForwardFocus ON) and SCAN 2 (ForwardFocus OFF).
2. To evaluate adult cochlear implant speech perception in quiet with the CP1170 sound processor and the CP1150 sound processor (commercial version).
3. To compare subjective acceptance and satisfaction between the CP1170 sound processor and the subject's own processor.
4. To compare adult cochlear implant subjective hearing performance between the CP1170 sound processor and the subject's own processor.

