7.3.2.5 Take-Home Period(s)

Take-home periods refer to blocks of time where the subject will use the IMD and associated accessories as their full-time device for a minimum of 2 weeks. The purpose of this is to allow actual use in the home environment. Should the subject report DD(s) within this time (via provoked or unprovoked feedback), the take-home period may be paused or stopped, allowing subjects to return to using their own sound processor until the DD can be investigated or resolved. There will be at least one take-home period between Visit 1 and Visit 2 and may be repeated as part of Ad-Hoc Visits until EOS.

During take-home periods, all subjects will be provided with SCAN 2 FF (automated ForwardFocus ON) as Program 1, and a SCAN 2 (user-controlled ForwardFocus, no automation) as Program 2.

While there are no expected unplanned product changes, early product can be sensitive to the low-risk issues identified in Table 4. During this study these product issues may be identified by study subjects during the in-clinic testing sessions that require optimisation or correction, and an adaptive procedure allows for product feedback to be collected from study subjects, for the product to be updated, and for the updated product to be reissued to study subjects for continued testing. Table 4 identifies how issues will be investigated and retested by the research subjects.

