9.2.2 Secondary Endpoints

1. Paired difference in dB SRT (AuSTIN) between the CP1170 SCAN 2 FF (Automated ForwardFocus ON) and CP1170 SCAN 2 (ForwardFocus OFF) in 65 dB SPL SON3 babble.
2. Paired difference in percentage CNC Words correct in quiet (50 dB) with the CP1170 sound processor and CP1150 sound processor.
3. Ratings based on the CP1170 Questionnaire after a minimum 2-weeks actual-use of the CP1170 sound processor in the home environment and the subject's own processor (Baseline Questionnaire).
4. Paired difference in Global SSQ12 scores after experience with the CP1170 sound processor and own processor (baseline).

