9.3.2 Secondary Hypotheses

Endpoint 1: Paired difference in dB SRT (AuSTIN) between CP1170 sound processor programs, SCAN 2 FF (Automated ForwardFocus ON) and SCAN 2 (ForwardFocus OFF). in 65 dB SPL SON3 babble. A non-inferiority margin of 1 dB is chosen based on clinical consensus.

H_0 : Sentence in noise (SON3) scores (dB SRT) with the Kanso 3 with SCAN 2 FF (treatment) are inferior to those with the Kanso 3 with SCAN 2

$Kanso\ 3\ SCAN\ 2\ FF\ ON - Kanso\ 3\ SCAN\ 2\ (ForwardFocus\ OFF) \geq 1\ dB$ (*NB: higher SRT scores represent poorer performance*)

H_1 : Sentence in noise (SON3scores (dB SRT) with the Kanso 3 with SCAN 2 FF ON (treatment) are inferior to those with the Kanso 3 with SCAN 2 (ForwardFocus OFF)

Kanso 3 SCAN 2 FF ON – Kanso 3 SCAN 2 (ForwardFocus OFF) < 1 dB

Endpoint 2: Paired difference in percentage CNC Words correct in quiet (50 dB) with the with the CP1170 sound processor (presented as Kanso 3 in the hypotheses) and the CP1150 sound processor (presented as Kanso 2 in the hypotheses). A non-inferiority margin of -10% is chosen based on clinical consensus.

H_0 : Words in quiet (50 dB CNC words) scores (% words correct) with the Kanso 3 (treatment) are inferior to those with the Kanso 2.

$CP1170 \text{ (Kanso 3)} - CP1150 \text{ (Kanso 2)} \leq -10\% \text{ (NB: lower CNC words represent poorer performance)}$

H_1 : Words in quiet (50 dB CNC words) scores (% words correct) with the Kanso 3 (treatment) are non-inferior to those with the Kanso 2.

$CP1170 \text{ (Kanso 3)} - CP1150 \text{ (Kanso 2)} > -10\%$

Endpoint 3: Paired difference in Global SSQ12 scores after experience with the Kanso 3. CP1170 Sound Processor (presented as Kanso 3 in the hypotheses) compared with the subject's own processor. A non-inferiority margin of -1 is chosen based on clinical consensus.

H_0 : Hearing performance ratings (SSQ12) with the CP1110 Sound Processor (treatment) are inferior to those with subject's own processor (control)

$Kanso 3 - \text{Own Processor} \leq -1 \text{ (NB: lower scores represent poorer performance)}$

H_1 : Hearing performance ratings (SSQ12) with the CP1110 Sound Processor (treatment) are non-inferior to those with subject's own processor (control)

$Kanso 3 - \text{Own Processor} > -1$

No formal hypotheses are specified for the following secondary endpoint:

- Ratings on the CP1170 Questionnaire.

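### Does testing words in quiet only with ForwardFocus OFF leave the CP1170 versus CP1150 comparison mis-specified?

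*Combined protocol and SAP*

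**What the plan says.** The endpoint in Section 9.2.2 is "Paired difference in percentage CNC Words correct in quiet (50 dB) with the CP1170 sound processor and CP1150 sound processor". The alternative hypothesis in Section 9.3.2 is that "scores (% words correct) with the Kanso 3 (treatment) are non-inferior to those with the Kanso 2", with a margin of -10 percentage points. Secondary objective 2 in Section 6.2 also names only the two processors. None of the three gives a program or a ForwardFocus setting.

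Section 7.3.2.2 supplies both. It says booth testing in quiet uses the combinations in Table 3. The treatment row reads "Kanso 3 (CP1170) ✓ SCAN 2 OFF"; the control row is Kanso 2 with SCAN and ForwardFocus OFF. The column holding SCAN 2 and SCAN is headed as the default. Each condition uses two 50-word CNC lists, and the CNC test order in Section 7.2.7 concerns these two conditions only.

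SCAN 2 FF is booth-tested in noise only (Table 2, Section 7.3.2.1). At home it is the first program: "all subjects will be provided with SCAN 2 FF (automated ForwardFocus ON) as Program 1" (Section 7.3.2.5).

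**The concern.** For the primary endpoint and the first secondary endpoint, the objectives, endpoints and hypotheses name the programs being compared. The words-in-quiet endpoint is the exception among the booth tests with a formal hypothesis. Section 4.3 puts particular focus on automated ForwardFocus and lists monosyllabic words in quiet as a key indicator of performance, yet the automated program is never scored on such words.

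The earlier evidence in Section 4.2.2.1 is mixed. One study found: "For CNC words in quiet ForwardFocus Strong was inferior to the Nucleus 6 SCAN". Another found: "Word recognition scores in quiet and questionnaire ratings for all ForwardFocus programs were comparable to N6 SCAN". The protocol does not say whether the automation can engage ForwardFocus for 50 dB SPL speech in quiet, so equality of SCAN 2 FF and SCAN 2 in quiet cannot be assumed from it.

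At stake is the scope of the conclusion. A finding that Kanso 3 is non-inferior to Kanso 2 in quiet, or superior if the later test in Section 9.6.2 succeeds, could be taken to cover a program that contributed no word scores.

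**Working it through.** **1. Is the tested condition determined?** The sections fit together as follows.

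| Place | Treatment | Control |
|---|---|---|
| 6.2, 9.2.2, 9.3.2 | CP1170 / Kanso 3 | CP1150 / Kanso 2 |
| 7.2.7, CNC order | Kanso 3 | Kanso 2 |
| 7.3.2.2, Table 3 | Kanso 3, SCAN 2, ForwardFocus OFF | Kanso 2, SCAN, ForwardFocus OFF |
| 9.6.2, decision rule | the treatment condition | the control |

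The general statements are silent on program, and Table 3 fills the silence. Nothing contradicts it. A tester following Section 7.3.2.2 can run only one pair of conditions, and an analyst has only one pair of scores per subject to difference.

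**2. Is the comparison valid?** ForwardFocus is OFF and SNR-NR is on for both processors, so the paired difference compares processors on their default programs. Section 7.1 gives this as the reason for acute use of Kanso 2.

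**3. The plan's own sample size.** It concerns speech in noise, not words. Inputs from Section 9.4: margin 1 dB, SD of the paired difference 1.36 dB, one-sided alpha 0.025, power 0.80. Power of the paired t test at true difference 0 comes from the noncentral t with n - 1 degrees of freedom and noncentrality 1 × √n / 1.36.

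- n = 16: 0.785
- n = 17: 0.812
- Attrition: 17 / 0.85 = 20

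The planned 17 and 20 reproduce. The documents give no SD or power for CNC words.

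**4. What would a SCAN 2 FF word condition add?** The SD of the paired difference must be assumed. Binomial variation alone, for two 100-word scores at 50% correct, gives √(2 × 0.25 / 100) = 7.07 points; at 80% correct it gives √(2 × 0.16 / 100) = 5.66. The range 7.07 to 15 is used below. With n = 17 and t(0.975, 16) = 2.120, the half-width of the 95% interval is 2.120 × SD / √17. The chance that the lower limit exceeds -10 uses noncentrality (d + 10) / (SD / √17), where d is the true difference in points.

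| Assumed SD | Half-width | Chance, d = 0 | Chance, d = -5 |
|---|---|---|---|
| 7.07 | 3.64 | 1.00 | 0.78 |
| 10 | 5.14 | 0.97 | 0.49 |
| 12 | 6.17 | 0.90 | 0.37 |
| 15 | 7.71 | 0.73 | 0.25 |

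These figures describe a condition that is not planned. They do not measure any error in the planned endpoint.

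**5. What would it cost?** The CNC session would grow from 4 lists to 6, or 200 words to 300. Section 7.3.4 requires all comparisons for an endpoint on one day, so a subject already tested would repeat everything and hold two sets of scores for the endpoint. Section 9.5 builds the per-protocol set on one set of paired measurements and treats departure from the intended order as a violation. Moving from two test orders to six part-way through would complicate both.

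**The case for a change.** The strongest case for a change is that naming the program costs little, matches how the plan words its other booth endpoints, and removes an ambiguity before results are known. Because SCAN 2 FF is the first take-home program, a device-level claim would naturally be taken to include it. Self-report measures do not replace a word score. Version 3 already added a third speech-in-noise condition after recruitment was complete, and the words-in-quiet endpoint is not among those listed for the interim analysis in Section 9.8.

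Part of this stands. The planned word scores cannot support a statement about SCAN 2 FF in quiet in either direction, and the clinical investigation report should not make one. But copying the Table 3 settings into four other sections changes neither the test nor the analysis, and under Section 18 a change to the protocol goes through a documented amendment with ethics committee notification.

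The evidence of risk is thin. The unfavourable earlier result concerned ForwardFocus Strong against Nucleus 6 SCAN, not automated ForwardFocus on Kanso 3, and the investigators of that study still concluded that "the risk versus benefit profile is acceptable when ForwardFocus be used in quiet environments". Everyday listening with SCAN 2 FF is covered, though subjectively, by the CP1170 Questionnaire, SSQ12, APHAB and EMA. EMA records both the program in use and the level of background sound. Table 4 also lets complaints about sound in quiet rooms lead to a product update and repeat speech testing. That fits a study whose stated focus for the automation is acceptance and satisfaction.

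**Conclusion.** No change to the plan is needed. The general wording is a gap that Table 3 already fills, and leaving SCAN 2 FF out of the quiet test is a fair trade-off for a comparison whose purpose is processor against processor. The effect on the estimate, confidence interval and error rate of the words-in-quiet endpoint is nil.

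The limit on scope is real: 100 words in each ForwardFocus OFF condition and 0 with SCAN 2 FF per subject. It is met by describing the result as Kanso 3 SCAN 2 against Kanso 2 SCAN, both with ForwardFocus OFF.

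This rests on two assumptions: that testing follows Table 3, and that the report states the tested condition. It does not rest on SCAN 2 FF performing as well as SCAN 2 in quiet, which the documents neither show nor rule out.
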